The feasibility pilot on individuals with PD at BCI Laboratories (CCIT) will determine technology acceptance and possible clinical benefit for better arms/hands motor control (reduced tremor), as well as focusing. Results from this pilot will be the basis for a follow up larger study.

The BAC usability component will take place at Bright Cloud International Laboratories, CCIT (North Brunswick, NJ). It will generate data on ease of use of the system, technical issues, and may lead to software improvements;

The BAC feasibility study will take place at PowerBack in Piscataway, NJ and will give initial indication of technology acceptance, as well as clinical benefit in terms of improved motor and cognitive function, reduced upper body pain, as well as diminished depression (feasibility) of short term residents at a Post-Acute facility.

The randomised controlled trials will take place at Kessler Foundation (West Orange, NJ). It will develop a new longitudinal therapy for elderly stroke survivors who are inpatients and then outpatients at a regional rehabilitation hospital, by adding BAC training to customary care for both inpatients and outpatients. Two systems will be used, improving continuity of care (one each for inpatient and outpatient settings).

This Protocol has **split oversight**, with the usability and feasibility components being overseen by WIRB, and the RCT component being overseen by Kessler IRB (KIRB).

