While BrightArm Duo proved quite beneficial to patients, clinicians considered it too large for actual clinic use. The cost of the system was also a factor for its non-adoption in clinical sites. As a consequence, BCI has applied for and obtained further funding from NIH, to develop BAC. It is about half the size of its BrightArm Duo precursor, and a simplified architecture (that will reduce cost). The smaller and cheaper BAC (Figure 1) does not however short-change the patient. On the contrary, it integrates better tracking (replacing overhead expensive cameras with wireless VIVE tracker. More importantly, the novel hand controllers used to play BCI therapeutic games now also measure finger extension, as well as forearm pronation/supination.

Figure 1 BAC rehabilitation table: a) prototype at BCI Laboratories (CCIT); b) BBG controller measuring position, grasp strength, finger extension and pronation/supination.

The BrightBrainer is a Class I medical device (listed with the FDA). It is a compact, mobile platform that currently is the subjects of Protocol 16-001 for home telerehabilitation of subjects chronic post-stroke living at home.

In the pilot feasibility study on individuals with PD, we will use the BrightBrainer (Figure 2) to attempt to reduce arm tremors and improve error rates and completion times in virtual reality tasks.

Figure 2. BrightBrainer system to be used in the pilot feasibility for individuals with PD

i. Why is this study being done?

The research project is intended to provide information pertaining to the usability, feasibility and clinical benefit of the *BAC* system for early sub-acute post CVA rehabilitation, improved cognition and emotive state while inpatient in short-term care facility settings (PowerBack Rehabilitation), in acute inpatient rehabilitation settings (Kessler Foundation) and in an outpatient clinic at the same research hospital. Specific aims are:

- BAC technology acceptance (all groups);
- improved motor function for upper extremity;
- strengthening shoulder and fingers
- increased range of motion for arms and fingers;
- improved independence in activities of daily living;
- improved cognition;
- improved emotive state;
- reduction in perceived upper body pain.

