The first BAC system will be installed at PowerBack and 6 participants 5 to 10 days post CVA admitted to inpatient rehabilitation will be recruited. They will train for up to 3 weeks, every other day, totalling up to 12 rehabilitation session playing a series of integrative exercises. Each session will start with a baseline for arm reach in the horizontal and vertical plane, pronation/supination range, as well as grasp strength and finger extension. These baselines will be used to adapt each game to an individual participant's motor impairment level in a given day, making the games winnable. Games

will produce congratulatory feedback, designed to maximize motivation, giving the subjects a feeling of control over their therapy and of accomplishment.

To combat boredom, new games will be added, such that the number of available games will progress from 4 games for sessions 1-4 to 6 games for sessions 5-8, and 8 games for sessions 9-12. The characteristics of each game will change from week to week (for example later-stage games will use dual-tasking involving moving and grasping simultaneously). Subjects will have a choice of games to play from among those available and will know the level they had achieved in a particular game.

The VR training will progress from 15 minutes/session of actual play (sessions 1-4), to 20 minutes (sessions 5-8) to 30 minutes (sessions 9-12). The BAC will be used in uni-manual mode providing training to the affected UE in sessions 1-4, and in bimanual mode for sessions 5-12. Furthermore, grasp and shoulder training will progress from no grasping required in sessions 1-4, to momentary grasping needed to play in sessions 5-12. Towards the end of training each session should induce >600 repetitions/arm, an amount consistent with inducing brain plasticity [Nudo 1997]. Subjects will play while supported by the BAC table in horizontal position. At the discretion of the therapist in the room, if moderate to mildly impaired participants tolerate, the table may be tilted up to 10 degrees.

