Before the start of a session the participant's blood pressure and pulse will be measured, to make sure it is safe to train that day. After the half-time mark is reached, the BAC system will automatically pause the session and ask for another reading of blood pressure and pulse. Once the prescribed game time is reached for a session, the game time is automatically ended by the system and the Therapist prompted to do one more blood pressure and pulse readings.

A remote database will store game performance data and allow access by the researchers following subject compliance to protocol and game performance progression. Subjects will be given the opportunity to make up any missed sessions.

At the end of sessions 4, 8 and 12 subjects will fill online subjective evaluation form rating their experience on the system. When logged over time these evaluations will give a measure of the subject's perceived value of the experience. Technology acceptance will also be gaged based on adherence to protocol.

At the end of Session 12 of a given subject, the OT will fill his/her custom evaluation form of the BAC system. The therapist will rate the ease of setting up sessions, the perceived benefit in terms of reduced work load, ease of notes entering, number of technical problems encountered, appropriateness of training intensity and overall satisfaction. Therapists will also have a log-book for noting session specific issues. Participants in the feasibility evaluation will not be paid.

Subsequent to the training of the 6 subjects at PowerBack, and based on their feedback we may fine-tune the BAC systems prior to deployment to the Kessler Foundation for the randomized control study.

Outcomes of feasibility study on individuals early post-stroke

Primary outcomes:

v. 7/8/2018

- The main motor outcome measure will be the FMA UE score, and success will be a group average score increase of 10 points or more, compared to baseline.
- The main outcome for the cognitive domain will be executive function improvement measured by Trail Making Test B (TMT-B) and the NAB Executive Functioning Module.

Secondary outcomes:

In the motor impairment domain secondary outcomes will be:

- increased arm range in pronation/supination (based on new games we will develop);
- grasp strength increase;
- finger extension range increase,
- increase in UEFI;

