- o **Data Analysis and Data Monitoring.** We will use repeated measures of ANOVA statistical analysis to look at the participants' data comparing pre-training conventional evaluation results with post-training results, to determine early indications of clinical benefit. We will also collect subjective evaluation questionnaires from each participant and from the occupational therapist (once post-training) on their impression of the system, its perceived benefits and shortcomings, its ease of use in a clinical setting. We will also collect data on Activities of Daily Living, using a standardised form, as well as data from caregivers so to gauge transfer of training to real life activities.

In order to gauge technology acceptance we will collect a subjective evaluation of the BAC from each participant in the experimental group. The scores (1 – least favourable outcome to 5 most favourable one) from each question will be averaged over the group. The BAC subjective evaluation forms will be collected twice (after 6 weeks of outpatient therapy and at end of outpatient therapy). By looking at the progression (or regression) of these scores, we will also be able to determine if ease of use of the technology increased with the accumulation of training sessions (or not).

All the data will be entered to the central data management system remotely.

- o **Data Storage and Confidentiality.** Each subject will have his/her name encoded such that the experimental and clinical measures will not log the participant's real name. The only mapping between the assigned encoded ID and the participant's real identity will be on the consent forms. These will be kept under lock by:

- 1) [name] OT and [name] for the participants early post-stroke PowerBack Rehabilitation;
- 2) [name] for the participants early post-stroke training at Kessler Foundation

The computerized data will be uploaded on a cloud secure database. Access to the database will only be granted to the research team, and will be password protected. Paper records involving the motor and cognitive evaluations as well as the subjective evaluation questionnaires will also be kept locked by [name] OT, [name], [name] (for the cognitive and emotive evaluations of the feasibility subjects) and [name] MD for the controlled trials subjects at Kessler Foundation.

- o **Transition from Research Participation.** Subjects will not have their standard of care or medication interrupted during participation.

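### RCT acceptance ratings are collected only from outpatient week 6 and compared as group averages, so drop-out can raise the score or look like progression

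*Protocol*

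**What the plan says.** Technology acceptance heads the list of specific aims under Why is this study being done? in the protocol, for all groups. The Purpose of the study section says that the PowerBack study "will give initial indication of technology acceptance, as well as clinical benefit in terms of improved motor and cognitive function".

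**RCT.** Under Data Analysis and Data Monitoring, acceptance is to be gauged from a subjective evaluation form completed by each experimental subject, on a scale of 1 (least favourable) to 5. The scores "from each question will be averaged over the group". The form is collected twice: after six weeks of outpatient therapy and at the end of it. The rise or fall of the scores between the two is to show whether the system became easier to use. No form is set for the inpatient phase or for a subject who stops.

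**Feasibility study.** Under Inpatient experimental therapy for the feasibility study: "They will train for up to 3 weeks, every other day, totalling up to 12 rehabilitation session". On ratings: "At the end of sessions 4, 8 and 12 subjects will fill online subjective evaluation form". The same section adds: "Technology acceptance will also be gaged based on adherence to protocol".

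Under Process of Consent, subjects may leave at any time. No drop-out rate is given.

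**The concern.** Whether a subject is present to fill in a form depends partly on what the form measures. Someone who finds the system tiring, frustrating or awkward is more likely to stop, and stopping removes that person's later ratings.

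Two separate errors can follow in the RCT:

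- **Level.** Subjects who stop before outpatient week 6 never enter either average, so both describe only those who stayed.
- **Progression.** Subjects who stop between the forms count in the first average and not in the second. The difference then mixes real change with a change in who answered, and the protocol reads it all as change in ease of use.

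At stake is a stated aim and the sponsor's account of how well the device is tolerated early after stroke, the period in which rejection would be most informative. The RCT's primary outcomes (FMA and executive function) are not affected.

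**Working it through.** The protocol gives no target, threshold, variance or drop-out rate for acceptance, so there is no stated figure to reproduce. The inputs from the protocol are:

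- experimental group n = 10 (RCT, Subject Recruitment) and feasibility n = 6;
- up to 12 inpatient sessions, then 2 to 3 outpatient sessions a week for 2 to 3 months (RCT, Experimental group);
- the form times given above.

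Scores and numbers stopping are assumptions.

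**1. Exposure before the first RCT form.** Six weeks at 2 to 3 sessions a week is 6 × 2 = 12 to 6 × 3 = 18 outpatient sessions. With up to 12 inpatient sessions, the first rating follows up to 12 + 12 = 24 to 12 + 18 = 30 BAC sessions. A subject who stops before then has no scheduled rating.

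**2. Overstatement of the level.** Let k of n subjects give no form, with mean rating c among those who stay and s among those who stop (the rating they would have given). The observed mean is c and the mean over all enrolled is [(n − k)c + ks]/n, so

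overstatement = (k/n)(c − s).

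With c = 4.5 and k = 2:

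| Study | s = 2 | s = 3 | s = 4 | s = 4.5 |
|---|---|---|---|---|
| RCT, n = 10: all-enrolled mean | 4.00 | 4.20 | 4.40 | 4.50 |
| RCT: overstatement | 0.50 | 0.30 | 0.10 | 0 |
| Feasibility, n = 6: all-enrolled mean | 3.67 | 4.00 | 4.33 | 4.50 |
| Feasibility: overstatement | 0.83 | 0.50 | 0.17 | 0 |

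The feasibility row applies only to subjects who stop before session 4, or to a later form read without the earlier ones.

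**3. Apparent progression in the RCT.** Suppose that at week 6 eight subjects score 4 and two score 2, that the two then stop, and that nobody changes their rating.

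- First form: (8 × 4 + 2 × 2)/10 = 36/10 = 3.6.
- Second form: (8 × 4)/8 = 4.0.
- Difference in group averages: +0.4, which equals (2/10)(4 − 2).
- Paired change in the eight with both forms: 4 − 4 = 0.

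The whole +0.4 comes from the change in respondents. The paired figure gives the right answer. If the same two stop before week 6, both averages are 4.0 and the 3.6 is never seen. Pairing cannot repair that case; only a rating taken at withdrawal can.

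**The case against.** The case against runs as follows.

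- **Ratings are secondary outcomes and carry no success threshold.** This stands and limits the weight of the point. The position at the head of the specific aims is in an unranked list, and the numbered aims at the start of the protocol begin with developing the system.
- **Scores and drop-out are invented.** This also stands. The protocol gives no rate, and the effect vanishes if nobody stops or if stoppers would have rated the system the same. The wording must be open to bias, not biased.
- **Other records exist.** An exit video interview is planned for all subjects training on the BAC (Debriefing Procedures), the feasibility therapists keep a log-book, and subject feedback is sought during outpatient therapy. These may capture the views of those who stop. None is linked to the 1 to 5 scores that are averaged, and the outpatient feedback also starts after the inpatient phase.
- **An analysis plan could settle this.** It could specify paired change. It could not recover a rating that was never collected, and the protocol fixes the form times.

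A reader might go further and infer that acceptance is also inflated through adherence, because the feasibility amount is "totalling up to 12 rehabilitation session" and "Subjects will be given the opportunity to make up any missed sessions". The text does not support this. It never says that a made-up session counts as adherent, and the section sets out a 12-session progression. Early stopping lowers adherence over all enrolled: if one of six stops after session 3 and the rest complete 12, it is (5 × 12 + 3)/72 = 63/72 = 87.5%. The exact definition is detail that an analysis plan can supply, and the adherence measure is not used in the RCT.

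**Conclusion.** The point holds for the RCT forms. Ratings begin only after up to 24 to 30 BAC sessions, none is set at withdrawal, and a difference between group averages is read as change in ease of use. The acceptance result is open to bias towards acceptance, and drop-out alone can appear as progression. If two of ten stop, the overstatement is 0.1 to 0.5 points on the 1 to 5 scale when those who stay average 4.5 and those who stop would score 4 down to 2. In the example above the false progression is 0.4. It is zero without drop-out related to opinion.

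The feasibility study has the same gap in milder form. Anyone who stops after session 4 or 8 has already given a rating, so mainly those who stop before session 4 are lost.

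It does not follow that the plan cannot show non-acceptance. Low ratings from those still in training at week 6 would be seen (the 3.6 in the example includes the two dissatisfied subjects), and in the feasibility study early stops can show in adherence. This is a cheap improvement to a secondary measure.

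**What to change.** Three changes, to Data Analysis and Data Monitoring and to the feasibility section where it applies:

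1. Any subject training on the BAC who stops, in either study, completes the same rating form at the last session attended. Report these ratings beside the scheduled ones, marked as withdrawal forms.
2. Report the number of respondents at each time point against the number enrolled (10 in the RCT experimental group, 6 in the feasibility study).
3. Base any statement on progression on within-subject paired change, not on the difference between group averages. A subject who stops after the first RCT form contributes that form and the withdrawal form as a pair.

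The cost is one extra short form at withdrawal, using an existing instrument. The downside is a possibly less favourable acceptance score, and some subjects who stop may decline the form; the respondent counts would show how many.

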1. **Background:** Patients who are in the chronic phase (> 9 mo) post stroke have been shown to improve if they train intensively and for long duration. This rehabilitation needs to be done in a task-oriented way, provide knowledge of performance to the patient, while making sure the patient is focusing on the exercise. Patients who are in the sub-acute phase post-stroke (< 6 months from the event) have weaker arms, and typically receive less upper extremity training. This is especially true in the early sub-acute phase (5+days after CVA) when the brain exhibits hyper plasticity. These patients could benefit from a system such as BAC, which modulates gravity bearing on the affected arm. At the same time they may benefit from neural rewiring or brain plasticity that is induced by a large number of task-oriented arm repetitions. The Principal Investigator, [name], has conducted pilot studies of advanced rehabilitation technology on several patient populations over the past 10+ years. In his previous capacity as Post-Doctoral Fellow at Kessler Foundation (the same clinical site we will use) and Research Associate at Rutgers Biomedical Engineering Department, he developed a novel rehabilitation device for stroke patients and conducted a clinical research to assess and improve visuo-motor targeting function which translated to activities of daily living (ADLs). At Bright Cloud International [name] is overseeing several studies involving the type of custom virtual rehabilitation games that will be developed for the patient population in the current study.

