Sessions will be interspaced with days when the programmer and engineer will address issues uncovered in the previous session(s). The process will be repeated in the subsequent 2 weeks with the other 2 volunteers. The Usability study will inform improvements necessary in the BAC system prior to feasibility study.

Feasibility Study (PowerBack Rehabilitation)

This will be an ABA protocol, with measures taken pre- (A), during experimental therapy (B) and post-intervention (A).

Participants Recruitment

6 elderly sub-acute post-CVA admitted to PowerBack for inpatient rehabilitation will be recruited. Participants will be pre-screened through a script questionnaire and MoCA screening. Those who met inclusion criteria will be consented by [name] OT (Co-Investigator and Director of Rehabilitation at PowerBack).

Participants standardised evaluations for feasibility study

Before the VR training (A) all participants will be evaluated by a senior occupational therapist (OT). The OT will evaluate:

- UE FMA,
- Jebsen test of hand function [Jebsen 1969],
- bimanual activities CAHAI-9 [Barreca 2004]),
- UE active range of shoulder movement - goniometer,
- shoulder strength -wrist weights,
- grasp and pinch strength -dynamometer and pinch meter), and
- independence in ADLs (upper extremity functional index [Stratford et al, 2001]).
- Blood Pressure and Pulse.

Pre-experimental therapy, a neuropsychologist, blinded to the intervention, will perform the cognitive/emotive evaluations. We will assess:

- emotive state (via the Beck Depression Inventory II),
- verbal and visual attention (with the Neuropsychological Assessment Battery NAB),
- processing speed (with the Trail Making Test A [Heaton 1991] - TMT),
- verbal and visual learning and memory (with the Hopkins Verbal Learning Test, Revised (HVLN-R) [Brandt 2001] and the Brief Visuo-spatial Memory Test, Revised (BVMT-R) [Benedict 1997]), and
- executive function with the Trail Making Test B (TMT-B) and the NAB Executive Functioning Module.

The initial evaluations will serve as baseline for all participants. Subsequent to the VR training on the BAC system, all feasibility participants will be evaluated again (A) for motor impairments and function, cognitive and emotive state for indication of clinical benefit. These clinical evaluations will be performed at the PowerBack.

Inpatient experimental therapy for the feasibility study

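### The uncontrolled feasibility study calls a 10-point mean FMA gain success, though recovery and usual rehabilitation alone could produce it at a rate the protocol leaves unknown

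*Protocol*

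**What the plan says.** The Protocol section on outcomes of the feasibility study in individuals early post-stroke makes the FMA upper-extremity score the main motor outcome and adds that "success will be a group average score increase of 10 points or more, compared to baseline". It gives no comparator, no confidence bound, no expected gain under usual care and no reason for choosing 10.

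The design is one group measured before, during and after training. On enrolment the Protocol says "6 participants 5 to 10 days post CVA admitted to inpatient rehabilitation will be recruited", and on exposure "They will train for up to 3 weeks, every other day, totalling up to 12 rehabilitation session". The FMA is part of the therapist evaluation done before training and repeated after it. The readings taken at each session are device measures of reach, pronation/supination, grasp and finger extension, not FMA. The paragraph on transition from research participation says that standard care is not interrupted.

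On interpretation, the purpose section says the feasibility study "will give initial indication of technology acceptance, as well as clinical benefit". The feasibility evaluations section and the Data Analysis and Data Monitoring section likewise treat pre/post change as an indication, or early indication, of clinical benefit.

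Two secondary outcomes carry thresholds of the same kind: at least 6 points on CAHAI-9, and an average fall of 5 points on the Beck Depression Inventory II.

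**The concern.** A change from baseline in a single group adds together three things: the device effect, the effect of concurrent rehabilitation, and spontaneous recovery. The last is likely to matter here, because the Background describes the entry window as the "early sub-acute phase (5+days after CVA) when the brain exhibits hyper plasticity". The protocol recognises the problem in the randomised study: the Control study Outcomes section plans recovery curves to tell natural recovery from gains due to training. The feasibility study has no control group and no repeated pre-training FMA readings from which a recovery trend could be estimated, so it has no means of doing the same.

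At stake is how a favourable result would be described. A mean gain of 10 points or more would count as motor success under the protocol's own rule, even if the device contributed nothing. Enrolling more patients would narrow the estimate but would not remove this confounding.

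**Working it through.** The protocol gives no operating characteristics for the rule, so there is no figure to reproduce. The check is how often the rule would be met with zero device effect.

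**Inputs from the Protocol**
- n = 6.
- Threshold: observed mean gain of at least 10 points over baseline.
- One FMA reading before and one after up to 3 weeks of training.

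**Assumed inputs (the Protocol gives neither)**
- m, the mean FMA gain from recovery plus usual care: 0 to 15 points.
- s, the SD of individual change: 5 to 12 points.
- Individual changes are taken as normally distributed.

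**Formula**

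P(success) = 1 − Φ((10 − m) / (s/√6))

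Example with m = 5 and s = 8: the standard error is 8/√6 = 3.27, z = (10 − 5)/3.27 = 1.53, and P = 0.063.

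| Background gain m | s = 5 | s = 8 | s = 10 | s = 12 |
|---|---|---|---|---|
| 0 | 0.000 | 0.001 | 0.007 | 0.021 |
| 5 | 0.007 | 0.063 | 0.110 | 0.154 |
| 8 | 0.164 | 0.270 | 0.312 | 0.342 |
| 10 | 0.500 | 0.500 | 0.500 | 0.500 |
| 12 | 0.836 | 0.730 | 0.688 | 0.658 |
| 15 | 0.993 | 0.937 | 0.890 | 0.846 |

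The result is driven mainly by m. When m equals the threshold, the chance is one half whatever the SD.

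**Precision of the mean gain**

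The 95% half-width is t(0.975, 5 df) × s/√6, with t = 2.571. It is 5.2, 8.4, 10.5 and 12.6 points for s = 5, 8, 10 and 12. An observed mean of exactly 10 with s = 8 would have an interval of about 1.6 to 18.4.

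The rule also errs in the other direction. If the true total gain is 12 points and s = 8, it is missed with probability 1 − 0.730 = 0.27.

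**The case against.** **Nothing hangs on the rule.** No go/no-go decision, sample size or design choice for the randomised study is tied to the 10-point result. The Protocol says only that the system may be fine-tuned in the light of participants' feedback. This stands, and it limits the weight of the point.

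**The benefit claim is hedged.** The Protocol speaks of an initial or early indication, and the purpose section does not mention the threshold. This stands too. The hedge acknowledges a small study, however; it does not tell the reader that the gain is confounded with recovery and usual care.

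**A reader might infer that the rule cannot tell an effective device from an ineffective one, or that success is likely whatever the device does.** The documents do not support that. They give no recovery gain. With a background gain of 5 points the false-success chance is at most about 15% over the assumed SDs, and with none it is about 2% at most. It becomes large only if recovery plus usual care approaches 8 to 10 points or more. What can be said is that the error rate is unknown.

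**Acceptance is already measured.** Adherence is to be used to gauge it, and ratings are collected after sessions 4, 8 and 12. That is correct, but the ratings are secondary, adherence is not listed among the outcomes, and neither has a success criterion. The stated success rule sits on the question this design cannot answer.

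**The same rule in the randomised study matters more.** The Control study Outcomes section repeats the 10-point rule although a control group exists. That is a separate matter with a different remedy, and correcting it would leave the feasibility component as it is.

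**Conclusion.** The point holds as a fault in a stated rule. As written, 6 uncontrolled inpatients early after stroke could meet the motor success criterion through recovery and standard rehabilitation alone, and the Protocol gives no basis for judging how likely that is. Under assumed SDs of 5 to 12 points, the chance with no device effect runs from about 1–15% at a background gain of 5 points to 66–84% at 12. The mean gain is known only to within about 5 to 13 points either way. All of these figures rest on the assumed background gain, SD and normality; the confounding itself rests on none of them.

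The consequence is a possible misattributed statement of success. It is not a wrong confirmatory test, and the documents do not support reading it as a flawed gate to the randomised study. It should be corrected, but it does not threaten the trial.

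**What to change.** For the feasibility component only:

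1. Delete the 10-point success rule from the feasibility outcomes section, and treat the 6-point CAHAI-9 and 5-point Beck Depression Inventory II thresholds there in the same way.
2. Report these changes descriptively as means with 95% confidence intervals, labelled as not separable from natural recovery and standard care.
3. Amend the clinical-benefit wording in the purpose, feasibility evaluations and Data Analysis sections to say that, for this component, benefit is to be assessed by the between-group comparison in the randomised study.
4. Base any feasibility conclusion on the adherence and subjective ratings already collected, with the sponsor stating denominator and threshold in advance. The denominator needs attention: the Protocol allows up to 12 sessions, but strict alternate-day training over 21 days (days 1, 3, …, 21) gives 11. These statements must be reconciled.
5. Have the Control study Outcomes section define its own primary outcomes. It now points to the feasibility section, so steps 1 and 4 would otherwise leave a conflicting cross-reference. Its secondary outcomes are defined by the same kind of reference and need the same check.

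The cost is wording only, with no new data. The feasibility claim becomes less favourable.
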